9.5.2 Safety Meetings

The SMC will review safety data at pre-defined time points throughout the study, specifically: prior to commencing the first administration in the subsequent dose group (and ≥ 7 days of after the first R0.6C-administration of all subjects in the preceding dose-group). A minimum of two SMC meetings must take place: a meeting prior to initiation of the first 100 μ g R0.6C dose group (group 3), and a meeting after completion of follow up in all groups. The chair of

the SMC will determine for the other time points whether a meeting will be held, or whether a recommendation from all members may be formalized through e-mail. The frequency of these reviews may be adapted upon SMC recommendation if deemed necessary. An ad hoc SMC meeting may be convened at any time or at the request of the PI or local safety monitor to review safety data from subjects and/or groups who meet any of the holding rules as specified in the protocol (section 9.5.5) and SMC charter. If desirable, the SMC can have an additional meeting before the start of the trial, to discuss the protocol, the trial, future meetings and to have the opportunity to clarify any aspects with the sponsor.

9.5.3 Safety Reports

Safety reports will be prepared by the clinical investigator for review by the committee prior to each review. These reports will provide at a minimum the following information:

- Accrual data and subject status data with regard to completion of/discontinuation from the study.
- Summaries of solicited AEs, classified by severity.
- Unsolicited AEs (including SAEs), categorized by ICD-10 coding, severity and relatedness to study vaccine.
- Safety laboratory test results outside of normal institution reference ranges and considered clinically significant, classified by severity grading scale (irrespective of whether assessed as AEs).
- Any new or updated AEs that have met the holding rules.

The SMC will review the safety data within 2 working days. The SMC will summarize their recommendations to the study Sponsor as to whether there are safety concerns and whether the study should continue without change, be modified, or be terminated. If at any time a decision is made to permanently discontinue administration of study R0.6C administrations in all subjects, the Sponsor will notify the CCMO expeditiously.

The advice(s) of the SMC will only be sent to the Sponsor of the study. Should the Sponsor decide not to fully implement the advice of the SMC, the Sponsor will send the SMC advice to the CCMO, including a note to substantiate why (part of) the advice of the SMC will not be followed.

9.5.4 Inter-group progression

Progression to the next dosage group will depend in all cases upon a positive review by the SMC of safety data of the previous dosage group. The data to be reviewed before each dose group includes the safety data (solicited and unsolicited AEs through day 7 post R0.6C

administration) and clinically significant laboratory tests collected at 1, 2 and 7 days following R0.6C administration for all subjects in the specified dose group. The SMC will review the AEs (local, general, and laboratory) and will make recommendations regarding the continuation of the study for each group.

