4. STUDY DESIGN

This is a first-in-human, phase I, open-label, single-site, dose escalation study to determine the safety tolerability and immunogenicity of the R0.6C vaccine in two different adjuvant combinations. Administration of R0.6C to volunteers, follow up and clinical chemical, microbiological analysis and storage of the samples will take place in the Radboudumc in Nijmegen.

Thirty-two healthy adult volunteers will be recruited and divided over the study arms that will receive four vaccinations on days 0, 28, 56 and 168 with either 30 μ g or 100 μ g of R0.6C adjuvanted with Alhydrogel alone, or combined with Matrix-M (Table 1).

Three volunteers (Group 1A, n=3) will receive four vaccinations with the lower dose of 30 μ g R0.6C with Alhydrogel, and, in parallel, three volunteers (Group 1B, n=3) will receive four vaccinations with the lower dose of 30 μ g R0.6C with Alhydrogel and Matrix-M. Volunteers will be closely monitored for adverse events for a period of minimally 14 days after the first vaccination. If safe, an additional 5 volunteers per adjuvant arm (groups 2A and 2B) will then receive four vaccinations with the lower dose (30 μ g R0.6C). If considered safe following a minimum of 14 days of follow-up after the first R0.6C administration of groups 2A and 2B, three volunteers per adjuvant arm (groups 3A and 3B) will start the vaccination regimen with the higher dose of 100 μ g R0.6C. Finally, a minimum of 14 days after administration of the first vaccination in groups 3A and 3B, if considered safe, an additional 5 volunteers per adjuvant arm (groups 4A and 4B) will initiate the vaccination regimen with the higher dose of 100 μ g R0.6C. There will be no placebo group; TRA endpoints will be compared to pre-vaccination values. All volunteers will be followed up for adverse events until 84 days after the last immunisation. Total trial duration is approximately 8 months for each subject. Blood will be collected to assess the functional TRA, TBA and immunogenicity at pre-specified time points after R0.6C vaccinations (also see section 8.3.17). If one of the volunteers is considered not eligible for participation on day 0, an different ('back-up') volunteer will replace him/her. For this purpose up to two additional volunteers may be screened and kept as back up in each group.

Table 1: study arms.

Study arm	Number of volunteers	Candidate vaccine dose and adjuvant combination
1A	n=3	4x 30 μ g R0.6C Alhydrogel

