7.4 Summary of known and potential risks and benefits

7.4.1 Risk Assessment

The following section (Table 5) outlines the initial risk assessment and mitigation strategy for this study protocol.

Table 5. Risk Assessment and mitigation measures

Important potential/identified risk	Data/rationale for risk	Mitigation strategy
Investigational study product (R0.6C vaccine)		
Important potential risk: First-in-human unknown risk	There is no prior experience of R0.6C vaccine in human subjects.	Because of lack of in human experience, the vaccine will be administered with a staggered dose escalation step of two dosages (30 µg and 100 µg). Subjects will be observed closely by qualified clinicians, and emergency care will be immediately available to subjects. A minimum of 14 days is required between product administration to each group. Dose-escalation will be stopped if any of the safety holding criteria are met (section 9.5.5).
Important potential risk: Hypersensitivity (including anaphylaxis)	As with other vaccines, hypersensitivity and anaphylaxis to one or several components of the vaccine can rarely occur.	Subjects who report allergic reaction against constituents of the vaccine in the past will not be included. All vaccinated volunteers will be observed closely for at least 1 hour following administration of R0.6C with appropriate medical treatment readily available in case of severe adverse events.
Local and systemic reactogenicity to intramuscular administration of R0.6C	Generally, risks associated with vaccination include local inflammatory reactions to the injected product, such as pain and swelling at the injection site. Up to marked focal histopathological inflammation was reported in the animal toxicity studies, with partial recovery in recovery animals. Systemic effects generally associated with vaccination may include flu-like symptoms, fever,	Experienced and qualified medical personnel will administer the vaccination intramuscularly. Subjects will be informed about the local and systemic side effects that may occur and will be monitored closely for local and systemic adverse events. Subjects will be advised to inform or call the study doctor immediately if they experience any adverse events. Appropriate medication (e.g. paracetamol or antihistamines) for

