8.3.17 Schedule of trial visits and measurements

Study Day ¹	I-120 to I1-1	I1-1	I1	I1+1	I1+2	I1+7	I1+14	I2-1	I2	I2+1	I2+2	I2+7	I2+14	I3-1	I3	I3+1	I3+2	I3+7	I3+14	I3+28	I3+56	I4-1	I4	I4+1	I4+2	I4+7	I4+14	I4+28	I4+56	I4+84
Days after first R0.6C administration	N/A	N/A	0	1	2	7	14	27	28	29	30	35	42	55	56	57	58	63	70	84	112	167	168	169	170	175	182	196	224	252
Visit No.	1	2	3	4	5	6	7	8	9	10	11	12	13	14	15	16	17	18	19	20	21	22	23	24	25	26	27	28	29	30
Informed consent	•																													
Inclusion/exclusion criteria	•	•																												
Demographic data and medical history	•																													
Physical examination ²	• ²	• ²	• ²	• ²	• ²	• ²	• ²	• ²	• ²	• ²	• ²	• ²	• ²	• ²	• ²	• ²	• ²	• ²	• ²	• ²	• ²	• ²	• ²	• ²	• ²	• ²	• ²			
Height and weight measurement	• ²																													
Blood pressure, temperature, pulse ³	•	• ³																												
Record concomitant medication	•	•	•	•	•	•	•	•	•	•	•	•	•	•	•	•	•	•	•	•	•	•	•	•	•	•	•	•	•	
HIV, HBV, HCV	•																													
Pregnancy test (urine)	•	•																												
Drugs screening (urine)	•	•																												

Study Day ¹	I-120 to I1 -1	I1-1	I1	I1+1	I1+2	I1+7	I1+14	I2-1	I2	I2+1	I2+2	I2+7	I2+14	I3-1	I3	I3+1	I3+2	I3+7	I3+14	I3+28	I3+56	I4-1	I4	I4+1	I4+2	I4+7	I4+14	I4+28	I4+56	I4+84
Distribution of emergency card		•																												
Distribution of diary		•																												
R0.6C administration			•						•							•								•						
Solicited local AEs (days 0-7)			•	•	•	•	•			•	•	•	•			•	•	•	•					•	•	•	•			
Solicited general AEs (days 0-14)			•	•	•	•	•	•		•	•	•	•			•	•	•	•	•			•	•	•	•	•			
Unsolicited AEs (days 0-84)		•	•	•	•	•	•	•	•	•	•	•	•			•	•	•	•	•	•		•	•	•	•	•	•	•	
Complete blood count ⁴	•	•		•	•	•	•	•		•	•	•	•			•	•	•	•	•			•	•	•	•	•	•	•	
Biochemistry tests ⁵	•	•		•	•	•	•	•		•	•	•	•			•	•	•	•	•			•	•	•	•	•	•	•	
PBMC isolations and citrate plasma		•																											•	
Serology/ELISA		•						•															• ⁷	•				•	• ⁷	•
SMFA ⁸		•						•															•		•			•		•
Safety Report ⁹							• ⁸																						• ⁸	
End of study visit																														•
Daily blood volume (ml)	12	63	0	5	5	5	31	5	0	5	5	5	15	5	0	5	5	5	31	5	4	31	0	5	5	5	47	5	4	31
Cumulative blood volume (ml)	12	75	75	80	85	90	121	126	126	131	136	141	156	161	161	166	171	176	207	212	216	247	247	252	257	262	309	314	318	349

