1. Study days are represented as relative to the immunisation day. If an immunisation day takes place on a different day (+/-3 days is allowed for immunisation 2 and 3, +/-7 days is allowed for immunisation 4) the study visits related to that immunisation will shift accordingly. Moreover, following any given immunisation, for visits I#+7, I#+14 and I#+28 a relative window of +/-2 days is

allowed, for visits I#+56 and I#+84, a relative window of +/-10 days is allowed.

2. A physical examination including height and weight and vital parameters will be performed at the screening visit. On other visits, measurements may take place at the discretion of the physician.
3. Vital signs including body temperature, blood pressure and pulse will be recorded at the screening and inclusion visit. On other visits, measurements may take place at the discretion of the physician.
4. CBC test includes: hemoglobin, hematocrit, platelets, red blood cell count, MCV, white blood cell count + differentiation
5. Biochemistry test includes: creatinine, urea, sodium, potassium, bilirubin, AF, yGT, AST, ALT and LDH. Additional at screening: serology malaria (2mL), cholesterol, triglyceride and glucose (2mL).
6. For PBMC isolations and citrate plasma collection, timepoints I2+14, I4-1 and I4+84 are optional.
7. For serum samples collected at timepoints I3+56 and I4+56, +/-10 days is allowed.
8. SMFA assays will be performed with serum collected on minimally 3 time points (I1-1, I3+14 and I4+14). SMFA assays for other timepoints may not be performed if the results of I3+14 and I4+14 do not show significant transmission reduction compared to baseline (I1-1).
9. Safety report: A safety report will be prepared by the clinical investigator before initiation of a next group (2, 3 and 4), minimally 7 days after the first R0.6C administration in the preceding group. A safety report of all the safety data is made after the last study visit of group 4.

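### The SMC's minimum review package can close at day 7, although the next group may start only after at least 14 days of follow-up and a safety judgement

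*Protocol*

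**What the plan says.** Section 4 of the protocol sets the pace of escalation.

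- Group 1 to 2: "Volunteers will be closely monitored for adverse events for a period of minimally 14 days after the first vaccination", and group 2 follows if that proves safe.
- Group 2 to 3, the only step that raises the dose: "If considered safe following a minimum of 14 days of follow-up after the first R0.6C administration of groups 2A and 2B".
- Group 3 to 4: "a minimum of 14 days after administration of the first vaccination in groups 3A and 3B, if considered safe".

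The risk table in 7.4.1 repeats the interval: "A minimum of 14 days is required between product administration to each group".

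The committee's review is described separately, and its timing is built on day 7.

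- Section 9.5.2 allows the review once at least "7 days of after the first R0.6C-administration of all subjects in the preceding dose-group" have passed.
- Footnote 9 to the schedule in 8.3.17 allows the safety report "minimally 7 days after the first R0.6C administration in the preceding group".
- Section 9.5.4 makes progression conditional on a positive SMC review at every step. It lists the data as AEs through day 7 and "clinically significant laboratory tests collected at 1, 2 and 7 days following R0.6C administration for all subjects in the specified dose group".

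The SAP (Statistical interim analyses and stopping guidance) repeats that the SMC evaluates safety before the next group starts, but gives no cut-off day.

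**The concern.** The plan asks for 14 days of follow-up before each step, but the review that controls the step can be completed on the first 7. The second week is then waiting time whose data need not reach the committee before the next group is dosed.

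In a first-in-human trial the findings at stake are those too small to trigger a hold: a single or short-lived grade 3 event, a cluster of grade 2 events, or a laboratory change first seen at day 14. The step from group 2 to group 3 matters most, because antigen and both adjuvants rise together there. The other two steps add subjects at a dose already in use.

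**Working it through.** No power or alpha figure is involved. The check compares the two clocks and then does simple counting.

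**The two clocks**

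| Item | Day after first dose of the preceding group | Source |
|---|---|---|
| Earliest safety report | 7 | 8.3.17, footnote 9 |
| Earliest SMC review | 7 | 9.5.2 |
| AEs that must be in the package | through 7 | 9.5.4 |
| Laboratory panels that must be in the package | 1, 2, 7 | 9.5.4 |
| Systemic AEs solicited | through 14 | 9.2.2; 8.3.17, "Solicited general AEs (days 0-14" |
| Post-dose panels scheduled, as extracted | 1, 2, 7, 14 | 8.3.17 |
| Earliest dosing of the next group | 14 | 4; 7.4.1 |

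**What the required package leaves out, at most**
- AE days: 14 − 7 = 7 (days 8 to 14).
- Panels: 1 of 4 (day 14).
- The I1+14 visit has a ±2-day window (footnote 1), so it can fall on days 12 to 16. That is up to 16 − 14 = 2 days after the next group may be dosed.

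**Subjects at the dose-raising step**
- Group 2: 5 + 5 = 10. Group 1: 3 + 3 = 6. All at 30 µg: 16.
- Share affected: at most 10/16 = 62.5%.
- When group 3 starts, group 1 is at least 14 + 14 = 28 days past first dose, so the gap does not concern those six.
- Size of the step (section 6.1): antigen 100/30 = 3.3-fold, Alhydrogel 800/240 = 3.3-fold, Matrix-M 49/15 = 3.3-fold.

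These are upper limits. The 9.5.2 clock runs from the first dose of every subject in the group, and the documents do not say that all ten are dosed on one day. If dosing is staggered, earlier subjects are further along at the review. The review also has no latest date, so one held on day 14 or later is equally permitted.

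**What other routes cover on days 8 to 14**
- Holding rules (9.5.5): one related SAE, or two or more subjects with a related grade 3 event lasting more than 72 hours, stops dosing and brings an ad hoc SMC review. An event starting after day 11 (14 − 3) cannot have lasted that long by day 14.
- Local safety monitor (9.5.1), one of three SMC members: told of any probably or definitely related grade 3 event lasting more than 48 hours. A possibly related or shorter event is outside that notice, though the monitor also has a general role in reviewing severe events.
- Discretionary stops (9.5.5): the investigators, the safety monitor or the SMC can call for a hold at any time. This is a power to act; it does not oblige anyone to send the committee the data.

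**Delay if the cut-off moves to day 14**
- Assume that two working days of review (9.5.3) take 0 to 4 calendar days, 4 if a weekend intervenes.
- Shortest: data complete and reviewed on day 14, so 14 − 14 = 0 days.
- Longest on these limits: visit on day 16 plus 4 days = day 20, so 20 − 14 = 6 days.
- All three steps: 3 × 6 = 18 days at most on these limits. Report preparation is extra, and the documents give no time for it.

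**The case against.** The best defence is that this is a coherent two-layer design: an SMC review of the first week, followed by a further week under the holding rules. Every day-7 figure is a floor. Section 9.5.4 says what the data *include*, 9.5.3 describes minimum report content, and 9.5.2 and footnote 9 give earliest dates. The committee may therefore see later data, and its charter, which is not available, may require that. In the schedule as extracted, the first safety-report mark falls in the I1+14 column, which hints that day 14 was intended.

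Much of this stands. A reader might infer that section 4 and section 9.5 contradict each other. They do not, since both can be met at once. A reader might also infer that nobody is responsible for the judgement after 14 days. That does not hold either: 9.5.4 makes SMC review the gate at every step, so section 4 can be read as setting when and 9.5.4 as setting who. Nor is the second week unobserved. AEs are collected at every visit, by staff who can call for a hold.

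What remains is narrower. Permission to add data is not a requirement, and a day-7 package complies in full. The schedule mark cannot settle the matter: neighbouring rows are visibly misaligned (serology appears at I2-1 where the endpoints specify I1+14), and the footnote still allows day 7.

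**Conclusion.** The point holds in a limited form. The visible text does not require the SMC to review sub-threshold AEs from days 8 to 14, or the day-14 panel, before the next group is dosed. It concerns up to 10 subjects and up to 7 AE days each at the 30 to 100 µg step. At each of the other two steps it concerns up to 6 subjects, at an unchanged dose.

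It would go too far to say that serious safety signals could pass the committee unseen, because the holding rules apply on any day. No rate of missed findings can be given, since the documents contain no onset-time data.

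The conclusion rests on two assumptions: that the unseen charter sets no later cut-off, and that the day-14 blood count and biochemistry are scheduled as the extracted table shows. It is worth correcting because the data are already planned and the change is mainly wording.

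**What to change.** - In 9.5.2, 9.5.4 and footnote 9 of 8.3.17, set the SMC data cut-off at day 14 after first administration, at minimum for the group 2 to 3 step. The package should hold AEs through day 14 and panels from days 1, 2, 7 and 14 for all subjects still in follow-up.
- List any withdrawn subject or missed I1+14 visit in the safety report, and state that this does not block progression. Otherwise one absence could stall the trial.
- In section 4, cross-refer the safety judgement to the SMC review in 9.5.4.
- Align 8.3.9, which trains subjects to self-assess solicited general AEs for 7 days, with 9.2.2, which solicits systemic AEs for 14.
- Carry the same cut-off into the SMC charter.

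No new visit or test is needed, and an SMC meeting before group 3 is already mandatory. The price is about 0 to 6 days per changed step plus report preparation. Changing only the group 2 to 3 step incurs that once.

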9.5.5 Safety holding rules

The study may be placed on safety hold at any time for the following reasons:

- On advice of the safety monitor;
- On advice of the Principal/Clinical investigators;
- On advice of the SMC;
- On advice of the CCMO;
- If holding rules are met (see below).

If the following holding rules are met, administration of R0.6C will be held for all remaining administrations in that dosage group and subsequent groups:

- One or more participants experience a SAE that is determined to be at least possibly related to the administration of R0.6C
- Two or more subjects experience a grade 3 adverse event (local, clinical systemic or laboratory systemic) possibly, probably or definitely related to R0.6C administration and persisting at grade 3 for >72 hours

If considered necessary by the investigators or SMC, remaining administrations in lower dosage groups may also be put on hold.

The study site member first aware of the event meeting the holding rule will notify the Principal Investigator and the Local Safety Monitor. The PI will alert the appropriate parties. The SMC will be notified within 24 hours. An ad hoc SMC review will be performed. The following considerations must be discussed:

- Relationship of the AE or SAE to the study product
- Relationship of the AE or SAE to R0.6C dose
- Relationship of the AE or SAE to (one of) the adjuvants
- If appropriate, additional screening or laboratory testing is provided to other subjects to identify subjects who may develop similar symptoms
- If any study related SAE is not listed on the current informed consent form (ICF), the PI will revise the ICF and subjects will be asked to provide consent on the new ICF

R0.6C administration to subjects within the affected group and to the next (higher dosage) group may resume only if the local safety monitor, PI, SMC and the sponsor agree it is safe

to resume R0.6C administration. It may be decided to proceed with only R0.6C adjuvated with Alhydrogel (groups A) or only R0.6C adjuvated with Alhydrogel and Matrix-M (groups B). If the CCMO has recommended safety hold, re-initiation of the study will require CCMO concurrence. The CCMO will be informed of a safety hold by the sponsor. Following discussion, it may be decided to terminate the study.

All subjects who have received the study product will be followed for safety until resolution or stabilization (if determined to be chronic sequelae) of their AE(s). If at any time a decision is made to discontinue administration of study product in all subjects, expeditious notification will be provided by the Sponsor to the CCMO within 24 hours. The PI, local safety monitor, SMC or CCMO may stop or suspend the use of this product at any time.

10. STATISTICAL ANALYSIS

All data will be collected and verified prior to analysis. All data will be analysed in accordance with the Statistical Analysis Plan. Final analyses of all data will occur after study completion and final verification of data according to GCP. All data analyses will be conducted using IBM SPSS, R, SAS or Graphpad using the latest version available. Detailed statistical procedures, listings, table shells, and figures will be provided in a SAP prior to analysis. The SAP will be finalized before study close-out and database lock. The following key statistical components will be considered and a detailed description will be documented in the SAP:

- Primary and secondary endpoints and how they will be measured
- Statistical methods and tests that will be used to analyze the endpoints
- Strategy that will be used if the statistical test assumptions are not satisfied
- Indication of whether the comparisons will be using one-tailed or two-tailed *t*-test (with justification of the choice) and the level of significance to be used
- Identification of whether any adjustments to the significance level or the overall P-value will be made to account for any planned or unplanned subgroup analyses or multiple testing
- Specification of potential adjusted analyses and a statement with which covariates or factors will be included
- Planned exploratory analyses and justification of their importance
- Any subgroup effects with biological justification and support from within and outside the study

